01.7. Primary objective

To assess the Cost-effectiveness of a standardized weight loss method (Pronokal® Method) treatment to improve the health condition of obese patients with comorbidities and thereby reduce healthcare expenditure (pharmacological treatment, incidence of complications, use of health resources) and work absenteeism.

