- Renal profile: creatinine, glomerular filtration, creatinine clearance, microalbuminuria
- Nitrogen balance: urea, uric acid
- Thyroid profile: TSH, T3, T4
- Ionogram: Na, K, Cl, Ca, Mg

In the **initial visit (day 0)**: In this visit, a physical examination will be performed and data related to weight (weight, BMI, waist circumference), as well as data on comorbidities associated with obesity (type of pathology, pharmacological treatment, complications in the last year) will be recorded. After checking the inclusion/exclusion criteria, the patient information sheet will be given and the informed consent will be obtained. During this visit, the patient's quality of life will be assessed (with the SF-12 quality of life questionnaire) and treatment will be prescribed according to the method (PronoKal® Method), which will begin with phase 1 of the active stage.

PRONOCOST study. Cost-effectiveness pharmacoeconomic study of a standardized multidisciplinary weight loss method (PronoKal® Method) to improve health condition of obese patients with associated comorbidities.

In the **follow-up visits - Recorded by the doctor**. In the regular check-ups throughout the course of treatment, the physician will record: any discomfort or side effect related to weight loss treatment and whether there has been any change in the comorbidities associated with obesity (laboratory results, medication, complications, etc.). At the end of each stage the doctor will assess the patient's quality of life through a questionnaire.

In the **follow-up visits - Recorded by dietitians/nutritionists**. During the interviews that the dietitians/nutritionists will have with the patients, and parallel to the doctor's records, the following details will be recorded:

- Clinical data: anthropometric data and blood pressure
- Medication changes
- Onset of complications (e.g., hypertensive crisis, ...)
- Hospital admissions
- Work absenteeism: number of days and cause....

In case of early withdrawal from the study, the doctor will write the dropout date and the reason, in study completion form.

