10. STATISTIC ANALYSIS

10.1. Descriptive statistics

Descriptive statistics will be made of all the variables collected in the Case Report Form, building frequency tables for the nominal-type variables and measurements of central tendency and dispersion for continuous variables. The 95% confidence intervals (95% CI) will be estimated for the latter.

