10.2. Analysis of objectives

The primary objective analysis will include:

- Costs of weight loss treatment estimated from the cost of: protein products and dietary supplements + number of control visits + number of laboratory tests performed
- Healthcare expenditure estimated as the sum of the following costs: pharmacological treatment of associated comorbidities, incidence of

complications (visits to his/her primary care physician, a specialist or emergency department for acute complications, treatment of acute complications, number of hospital admission days, antibiotic treatment), consumption of health resources (visits to the general practitioner, visits to specialists, laboratory tests)

- Work absenteeism, estimate of the number of work leave days + hours of work absenteeism due to health problems or medical visits.

In order to evaluate if the weight loss treatment is improving the health of patients and reducing health expenditure and absenteeism, the healthcare expenses and work absenteeism estimated from the doctor's records corresponding to the 6 months prior to the initiation of the weight loss treatment will be compared with data recorded at follow-up visits over the 2-year follow-up. Likewise, the doses and number of drugs required by patients for the treatment of their comorbidities before the weight loss and at the control visits during weight loss and up to completing the 2 years of follow-up will be compared.

As secondary objectives, the efficacy of the weight loss treatment will be studied by comparing the anthropometric parameters of the initial visit with those of the follow-up visits (weight, body mass index and waist circumference). Likewise, any improvement in laboratory parameters and blood pressure during the follow-up will be studied. Changes in quality of life scores (SF-12) will also be assessed between the initial visit and the end of each treatment stage.

For all objectives, the comparisons between qualitative variables will be made using the Chi square test or the Fisher exact test, and the comparison between quantitative variables will be performed using the Student's t-test (in the case of 2 groups) or by the one-way ANOVA test (for 3 or more groups). If the conditions for the Student's t-test or the Anova test are not met, the non-parametric Mann-Whitney U test (2 groups) or the Kruskal-Wallis test (for 3 or more groups) will be used.

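### The primary objective is cost-effectiveness, but section 10.2 does not specify how programme cost is set against savings or joined to an effect, and leaves the 6-month and 24-month windows without a common time base

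*Combined protocol and SAP*

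**What the plan says.** Sections 1.7 and 3.1 give the primary objective as "To assess the Cost-effectiveness of a standardized weight loss method", with lower healthcare expenditure and less absenteeism as the expected consequence. Section 9.1 names resource use, drug changes and absenteeism as primary endpoints. Programme cost is not among them.

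Section 10.2 puts three items into the primary analysis:

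- programme cost, built from "protein products and dietary supplements + number of control visits + number of laboratory tests performed";
- healthcare expenditure, which sums comorbidity drugs, complications and "consumption of health resources (visits to the general practitioner, visits to specialists, laboratory tests";
- absenteeism in days and hours, with no monetary value attached.

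The comparison then opens "In order to evaluate if the weight loss treatment is improving the health of patients and reducing health expenditure and absenteeism, the healthcare expenses", and adds absenteeism. The doctor's records for the "6 months prior to the initiation of the weight loss treatment will be compared with data recorded at follow-up visits" through two years. Drug doses and numbers of drugs are compared in a similar way. Effects are handled apart: "As secondary objectives, the efficacy of the weight loss treatment will be studied by comparing the anthropometric parameters of the initial visit" with later visits, and SF-12 change is assessed by itself. The methods listed for all objectives are chi-square or Fisher tests, t-tests or ANOVA, and their rank-based substitutes.

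**The concern.** A cost-effectiveness question needs what the programme costs, what it saves, and what it achieves, all on one scale of time. Section 10.2 costs the programme and then leaves that figure unused. A significant fall in healthcare expenditure would be the natural headline, yet it would look the same whether the products and supplements cost less than the saving or several times more.

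A net cost or a cost per kilogram could still be worked out afterwards. Its form, its effect measure, its time base and its allocation of shared items would then be chosen with the data in hand.

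**Working it through.** The plan states no net cost, ratio, threshold or unit price, so there is no figure to reproduce. The check has a reading step and three small calculations.

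**1. Where each quantity is used**

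| Quantity | Listed | Used in |
|---|---|---|
| Programme cost | 10.2, primary analysis | no comparison |
| Healthcare expenditure | 10.2, primary analysis | before versus after |
| Absenteeism | 9.1 and 10.2 | before versus after, unpriced |
| Drug doses and number | 9.1 and 10.2 | before versus after |
| Weight, waist, SF-12 | 9.2, secondary | own change from the initial visit |

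No section combines the first row with any other, or any cost with the last row.

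**2. Netting (all amounts assumed)**

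Let H6 be healthcare cost in the 6 months before treatment, H24 that of the 24-month follow-up, P programme cost, and r the fall in monthly healthcare cost. With no item in both lists:

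- saving on a 24-month base = 4 × H6 − H24 = 4 × H6 × r
- net cost = P + (H24 − 4 × H6) = P − 4 × H6 × r

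With H6 = 100 units, the 24-month reference is 400:

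| r | Saving | Net, P = 20 | Net, P = 80 | Net, P = 200 |
|---|---|---|---|---|
| 10% | 40 | −20 | +40 | +160 |
| 20% | 80 | −60 | 0 | +120 |
| 30% | 120 | −100 | −40 | +80 |

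Within a row the planned comparison is identical, while the net result changes sign. At a net cost of +120, the price is 120/10 = 12 units per kg for a 10 kg loss and 120/20 = 6 for a 20 kg loss. The plan specifies neither calculation.

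**3. Time base (windows from 10.2; r assumed)**

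If totals are compared unscaled, with m the monthly cost before treatment:

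24m(1 − r) / 6m = 4 × (1 − r)

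| r | 0 | 0.30 | 0.50 | 0.75 |
|---|---|---|---|---|
| Ratio after/before | 4.0 | 2.8 | 2.0 | 1.0 |

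The ratio is below 1 only when r exceeds 0.75. In the example with H6 = 100 and r = 20%, H24 = 400 × 0.8 = 320. Unscaled, 320 against 100 reads as a rise of 220; scaled, 320 against 400 is a saving of 80.

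**4. Laboratory tests**

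Let L be the follow-up cost of tests done for the programme. Counted once, L enters net cost once. Counted in both lists, net cost is too high by L; left out of both, too low by L. Section 10.2 does not say which applies.

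**The case against.** The strongest reply is that programme cost is in the plan. Section 10.2 lists it in the primary analysis, section 10.1 promises that "Descriptive statistics will be made of all the variables collected in the Case Report Form", with 95% confidence intervals for continuous ones, and the primary objective itself mentions reducing expenditure and absenteeism, which the comparison does address. All of this stands. It is why a reader who infers that the plan cannot answer its primary objective goes too far: the ingredients are meant to be costed, and a net point estimate could be formed from them. What is missing is a specified form for it, a linked effect and an interval for the two together.

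Other stronger readings are also tempting, and the documents do not support them.

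- *Programme cost left out, so the method is flattered.* The time-base gap can work the other way, as step 3 shows. Without prices, the net direction is unknown.
- *Visits are double-counted.* Section 10.2 assigns control visits to programme cost, section 7.2 uses that term for its six scheduled visits, and healthcare expenditure names other kinds of visit. The clear overlap is laboratory tests. Day −15 and dietitian visits are merely unassigned.
- *The look-back windows conflict.* Section 7.2 records "type of pathology, pharmacological treatment, complications in the last year" at day 0, but section 10.2 already fixes 6 months for the costing. The one-year item is a wider history.
- *Costs after withdrawal are set to zero.* No section says so; section 7.2 has the dropout date recorded. The plan is only silent on the handling.

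**Conclusion.** The point holds as a gap in specification of the primary analysis, and it should be closed before the costs are analysed. Followed as written, section 10.2 tests whether expenditure, absenteeism and drug use changed. It does not specify how to judge whether savings exceed programme cost, or what each unit of effect costs.

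The reading in step 1 needs no assumption. The factor of 4 follows from the plan's own windows and matters if totals are compared; the plan does not say whether totals or rates are meant. The amounts in step 2 are assumed and show only that a fall in expenditure does not fix the sign of net cost. They do not estimate this trial's result, and neither the size nor the direction of any change in its headline can be given.

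**What to change.** Amend section 10.2 as follows.

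- **Net cost with an effect.** Add as the primary analysis, per patient: programme cost + (24-month follow-up healthcare cost − 4 × 6-month pre-treatment healthcare cost), or equivalently all costs per month. Report it jointly with one named effect already collected, for example kg lost at 24 months. Bootstrap cost and effect together by patient and give 95% confidence intervals.
- **Absenteeism.** Keep it in the primary analysis, in days and hours on the same time base. Give a monetised version as a sensitivity analysis.
- **Allocation.** Assign every laboratory test and visit delivered by the programme, including day −15 and dietitian visits, to programme cost only. Keep them out of healthcare expenditure and out of the scaled pre-treatment reference.
- **Complications.** Cost those before treatment from the 6-month window already set in 10.2, not from the one-year history item in 7.2.
- **Withdrawal.** State that healthcare cost after withdrawal is not counted as zero.
- **Interpretation.** Describe the result as an uncontrolled before-after estimate. Scaling by 4 takes the 6 months before treatment as typical of what would have followed.

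The cost is a set of unit prices and modest extra analysis work.

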4. STUDY DESIGN

Prospective, observational, multicenter study based on a registry of patients with obesity and associated comorbidities undergoing a standardized multidisciplinary weight loss method with a 2-year follow-up.

No randomization or administration of drug treatment is intended as a consequence of the patient's participation in the study.

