5. STUDY POPULATION

Obese patients with obesity-associated comorbidities treated with the standardized multidisciplinary weight loss method (PronoKal® Method).

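### The before/after comparison has no comparator and one 6-month baseline, so it can describe a change in costs and absence but cannot attribute that change to the method

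*Combined protocol and SAP*

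**What the plan says.** Section 4 describes a "Prospective, observational, multicenter study based on a registry of patients with obesity and associated comorbidities undergoing a standardized multidisciplinary weight loss method" and adds "No randomization or administration of drug treatment is intended as a consequence of the patient's participation in the study". Section 5 defines the population as patients treated with the method, so there is no untreated or otherwise treated group.

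The primary objective (Sections 1.7 and 3.1) is causal in form: the method is to improve health and, through that, lower healthcare spending and absence from work. Section 10.2 carries this into the analysis. The comparison is made "In order to evaluate if the weight loss treatment is improving the health of patients and reducing health expenditure and absenteeism". The baseline for expenses and absence is "estimated from the doctor's records corresponding to the 6 months prior to the initiation of the weight loss treatment", and it "will be compared with data recorded at follow-up visits over the 2-year follow-up". Drug doses and numbers of drugs are also compared before and during follow-up, with no look-back length stated.

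The methods named in Section 10.2 are chi-square or Fisher tests, t-tests or one-way ANOVA, and rank-based alternatives, at the 0.05 level. There is no external control, second pre-treatment period, trend model, covariate adjustment or sensitivity analysis, and no statement limits the causal reading.

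Three other places bear on this:
- Section 7.1 recruits consecutive patients at the point of attending the clinic and being prescribed the method.
- Section 5.1 refers to treatment with two or more drugs, and Section 9.1 makes change in drug treatment a primary endpoint.
- Section 7.2 has the day 0 visit record "complications in the last year". This is the only longer look-back, and the Section 10.2 comparison of costs and absence does not use it.

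**The concern.** A cost-effectiveness result depends on what costs would have been without the method. With no comparator, the plan implicitly sets that at the level seen in the 6 months before start, and neither states nor tests the assumption.

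It is open to doubt for three reasons. First, the baseline window ends when the patient seeks care, and entry may depend on drug use, which is also an outcome. Either can select patients at a temporarily high level, and a fall then follows without any treatment effect. Second, one 6-month block cannot show whether costs were stable, rising or at a peak. Third, the two periods are observed differently: the baseline comes from doctor's records, and follow-up from scheduled doctor and dietitian contacts. Costs may also drift over 2 years for unrelated reasons.

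A significance test does not separate these explanations from a treatment effect. At stake is whether the primary conclusion can be read as a saving caused by the method.

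**Working it through.** **The plan's own figure.** The only design figure is the expected 200 patients (Section 5.3). No effect size, SD, power or dropout is given, so it cannot be reproduced. It is used below only as the sample size.

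**Inputs.** From the documents: n = 200 and significance level 0.05 (taken as two-sided, critical value 1.96; the plan does not state sidedness). Assumed, with no source in the documents: zero treatment effect; patients selected on an observed baseline d = 0.3 to 0.5 SD above the population mean; before/after correlation r = 0.3 to 0.9; equal SDs before and after; normal data; both periods on a common time base.

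**Formulae, in SD units.**
- Expected fall from regression to the mean: d(1 - r).
- Standard error of the mean within-patient change: SE = sqrt(2(1 - r)/200).
- Paired test: probability of a significant fall = Φ(d(1 - r)/SE - 1.96).
- Unpaired test, as named in Section 10.2 for two groups: it needs a fall of 1.96 × sqrt(2/200) = 0.196, while the true variability of the change is still SE. Probability = Φ((d(1 - r) - 0.196)/SE).

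**One case in full.** With r = 0.5, SE = sqrt(1/200) = 0.0707. For d = 0.3 the fall is 0.15 and the ratio 0.15/0.0707 = 2.12. The paired probability is Φ(0.16) = 0.56, and the unpaired is Φ((0.15 - 0.196)/0.0707) = Φ(-0.65) = 0.26. For d = 0.5 the fall is 0.25 and the ratio 3.54, giving 0.94 and 0.78.

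**All cases (d = 0.3 to d = 0.5).**

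| r | Expected fall (SD) | SE | Paired | Unpaired |
|---|---|---|---|---|
| 0.3 | 0.21-0.35 | 0.0837 | 0.71-0.99 | 0.57-0.97 |
| 0.5 | 0.15-0.25 | 0.0707 | 0.56-0.94 | 0.26-0.78 |
| 0.7 | 0.09-0.15 | 0.0548 | 0.38-0.78 | 0.03-0.20 |
| 0.9 | 0.03-0.05 | 0.0316 | 0.16-0.35 | about 0 |

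The nominal rate in that direction is 0.025.

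**Cross-check by simulation** (2,000 runs per case, n = 200, zero effect). If entry is from the upper 80% of the baseline distribution, the mean excess is 0.35 SD. For r = 0.3, 0.5, 0.7 and 0.9, a significant fall appears in 0.88, 0.73, 0.50 and 0.21 of runs with the paired test, and in 0.81, 0.51, 0.15 and 0.00 with the unpaired test. With no selection the paired rate is about 0.025. The pattern is the same: the result depends mainly on r and on how strongly entry selects.

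**What the premise means.** The formula d(1 - r) applies to an excess over the population mean. If d were instead an excess over each patient's own usual level, the whole 0.3-0.5 SD would be expected to disappear, and the probabilities at r = 0.5 would be 0.99 to about 1.00 (paired) and 0.93 to about 1.00 (unpaired). The documents support neither value of d.

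**The case against.** The strongest defence is that this is openly an observational registry. Section 10.2 sets out to evaluate whether there is a reduction, applies a test, and claims no saving in advance. That is fair, and a control group is not asked for here. It does not answer the point, because the stated question concerns the effect of the treatment and nothing in the analysis or its reporting limits the answer to a description.

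Four stronger readings are tempting, and the documents do not support them:
- *A reader might infer that a fall is expected anyway, so any saving will be spurious.* The direction cannot be derived. Section 2 describes rising obesity-related costs at population level, and fuller capture at frequent follow-up contacts could raise recorded costs. Either could hide a real saving.
- *A reader might take one row of the table as the size of the bias.* Neither d nor r is in the documents, and r probably differs by outcome. Long-term drug use is likely to be stable (high r, small effect); admissions, acute complications and absence are episodic (lower r, more exposed). Cost data may also be far from normal, and Section 10.2 itself allows for rank tests.
- *A reader might infer that a year of baseline data is already collected.* The 12-month item in Section 7.2 covers complications only. Nothing shows that the records hold 12 months of costs and absence.
- *A reader might apply the 6-month limit to every primary variable.* It is stated for expenses and absence; the drug comparison has no stated window.

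The link between entry and drug use is also uncertain, because the two-drug wording in Section 5.1 does not make clear how it combines with the comorbidity list.

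**Conclusion.** The point holds in limited form. As planned, a significant before/after difference would be read as an effect of the method, and the design cannot carry that conclusion. Regression to the mean could produce an apparent saving; trends and differences in recording could bias the result in either direction. The size is unknown. Under the assumptions listed in the working, the chance of a significant saving with no treatment effect runs from 0.16 to 0.99 (paired) and from about 0 to 0.97 (unpaired). It is high where outcomes are weakly correlated over time. Where they are strongly correlated, it is close to zero for the unpaired test and still above nominal for the paired test. This is a reason to limit the claim and test the assumption behind it. It does not show that the study's result will be wrong.

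**What to change.** 1. In Sections 3.1 and 10.2, state the primary conclusion as a change from the pre-treatment period to follow-up. Label every cost-effectiveness figure as assuming that costs and absence would otherwise have stayed at the pre-treatment level.
2. Add a threshold analysis: show the net result over a range of non-treatment changes in cost, both falls and rises, and report the spontaneous fall that would cancel the saving. This needs no new data.
3. Where the doctor's records allow, extract months 7-12 before start as a second 6-month block, show both blocks, and repeat the comparison with the earlier block as baseline. Report how many patients have it. This can reveal a peak just before entry, but two blocks separate a trend only weakly.

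The cost is SAP wording, one extra analysis, some additional record review and a weaker headline claim.

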7.2. Follow-up period

The expected follow-up period for each patient will be 2 years from the time of inclusion, recording data during the weight loss and maintenance periods. The registry of patient data for this study will be made by the doctor and the dietitians/nutritionists who will regularly see the patient in the face-to-face visits at the Pronokal centre. For this, a specific form will be designed in which information about the variables to be studied will be collected.

Before starting treatment with the standardized multidisciplinary method and its inclusion in the study, the physician will have performed a first patient pre-inclusion visit (day -15) to request complementary tests (laboratory and ECG) and rule out the existence of contraindications to the ketogenic diet part of the weight loss program.

The study will begin with the baseline visit (day 0) in which the inclusion and exclusion criteria will be confirmed, the signing of informed consent will be obtained and the multidisciplinary treatment will be prescribed, followed by 6 control visits: 2 visits during the ketogenic stage (1-month after the start and at the end of ketosis), 2 visits during the physiological adaptation phase (at 4 or 5 months and at the end of stage 2) and 2 follow-up visits during the maintenance up to the 2-year completion. Regardless of the visits established in this protocol, the doctor will make as many visits as he/she deems necessary for good patient control.

On the other hand, dietitians/nutritionists, according to the methodology of the program, will carry out a face-to-face follow-up of the patient, which will be fortnightly during the ketogenic diet, monthly during the physiological adaptation of stage 2 and quarterly or semi-annual during the maintenance stage.

In the **pre-inclusion visit (day -15)**, the physician will perform a first clinical assessment of the patient. He/she will record the sociodemographic data, history of diabetes, comorbidities, pharmacological treatments. He/she will request complete laboratory tests and will perform an electrocardiogram to rule out contraindications and verify the inclusion/exclusion criteria. The said laboratory tests will include:

- Complete blood count and leukocyte formula
- Hydrocarbon metabolism: fasting glycemia, HbA1c, insulinemia
- Lipid profile: total cholesterol, LDL-C, HDL-C, triglycerides
- Transaminases: GOT, GPT, gammaGT

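### The primary before/after comparison takes its two periods from different sources, and section 7.2 names admissions and work absence only for the follow-up interviews

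*Combined protocol and SAP*

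**What the plan says.** Section 10.2 lists the components of healthcare expenditure once, including days in hospital, and defines absenteeism once, as days of leave plus hours lost. Neither definition is split by period. For the primary comparison, "the healthcare expenses and work absenteeism estimated from the doctor's records corresponding to the 6 months prior" to the start of treatment "will be compared with data recorded at follow-up visits over the 2-year follow-up".

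Section 7.2 says what is recorded at each contact:

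- **Day -15 (physician):** "He/she will record the sociodemographic data, history of diabetes, comorbidities, pharmacological treatments", plus laboratory tests and an ECG.
- **Day 0 (physician):** examination, anthropometry, SF-12, and comorbidity data described as "type of pathology, pharmacological treatment, complications in the last year".
- **Follow-up (physician):** side effects and "any change in the comorbidities associated with obesity (laboratory results, medication, complications, etc".
- **Follow-up (dietitian or nutritionist):** anthropometry and blood pressure, medication changes, complications, hospital admissions, and "Work absenteeism: number of days and cause". These interviews run "parallel to the doctor's records". They are fortnightly in the ketogenic stage, monthly in stage 2, and quarterly or semi-annual in maintenance.

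Section 7.2 also states that "a specific form will be designed in which information about the variables to be studied will be collected", and section 8.1 places the forms in Annex 3. Section 9.1 names admissions and work absenteeism among the primary variables to be recorded.

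**The concern.** The study is a single treated cohort (section 4), so the primary result is a difference between each patient's period before treatment and the same patient's period after. That difference is interpretable only if an event has about the same chance of being recorded in both periods.

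As written, the plan does not secure this for admissions and absence. In follow-up, a dietitian asks about them by name, repeatedly. For the 6 months before treatment, the values are estimated from the doctor's records, and no pre-treatment visit is told to ask about them. Absence from work is especially exposed, because a medical record need not hold it. Any shift in capture between the periods passes straight into the primary comparison, and no control group is present to absorb it.

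**Working it through.** The plan gives no event rates, costs or effect size, so there is no figure of its own to reproduce. The check sets the sections side by side and then illustrates the size.

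**Step 1. Sources (section 10.2).** Before: doctor's records, 6 months. After: data recorded at follow-up visits, 24 months. The quantities intended are the same; the stated sources differ.

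**Step 2. Where each item is named in section 7.2.**

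| Item analysed in 10.2 | Day -15 or day 0 | Doctor, follow-up | Dietitian, follow-up |
|---|---|---|---|
| Drug treatment | named | named | named |
| Complications | named (one-year history) | named | named |
| Hospital admissions | not named | not named | named |
| Work absence | not named | not named | named (days and cause) |

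Medication and complications have a counterpart in the doctor's records in both periods. Admissions and absence do not, unless admissions are read as part of complications.

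**Step 3. Whose records.** Section 7.2 describes day -15 as the physician's first clinical assessment of the patient, and section 10.2 refers separately to the patient's primary care physician. This suggests, without proving, that the study doctor may not hold a full record of the preceding 6 months.

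**Step 4. Illustration of size.** Let r be the true monthly rate, unchanged by treatment, and let c be pre-period capture as a fraction of follow-up capture. Rates are per month, so the unequal lengths of 6 and 24 months do not enter.

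Apparent change = r / (c × r) − 1 = 1/c − 1

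| c (assumed) | 1/c − 1 |
|---|---|
| 1.0 | 0% |
| 0.9 | +11% |
| 0.8 | +25% |
| 0.7 | +43% |
| 0.6 | +67% |
| 0.5 | +100% |

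The documents give no value for c. If c is below 1 the artefact is a rise and counts against the method. If c exceeds 1, for instance because records hold admissions that patients do not report at interview, the same formula gives a fall, which favours it.

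**Step 5. Look-back for complications.** Day 0 takes a 12-month history; section 10.2 uses 6 months. The longer window contains the shorter one, so dated events could be cut to 6 months. No sentence says that they are dated.

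**The case against.** The strongest case for the plan is that section 10.2 already applies one list of costs and one absenteeism definition to both periods and explicitly includes absenteeism in the 6 months before treatment. Extraction from medical records, which section 8.1 names as a source for the study, need not appear in a visit list. The lists in 7.2 and 9.1 are open-ended, the dietitians' recording runs alongside the doctor's, and section 9.1 names admissions and absence for recording. The Annex 3 form, the figure in section 7.1 and some text between sections 8.1 and 9 were not available, and any of them might supply the baseline items.

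Much of this stands. It rules out several stronger readings:

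- *The plan does not require the same items in both periods.* Section 10.2 does define common items. The gap is in how 7.2 provides for collecting them.
- *The one-year and 6-month look-backs contradict each other.* They do not; what is missing is an extraction rule. A reader might also infer an apparent 50% fall from using a 12-month count as a 6-month value (6/12 − 1), but section 10.2 does not direct that use.
- *The bias favours the method.* The direction is not determined by the documents.
- *Hours of absence are analysed but only days are listed in 7.2.* This is true, but it is a detail that the form could settle, not evidence of bias.

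What the objection does not remove is the sentence in 10.2 that assigns different sources to the two periods, together with the absence of admissions and work absence from both pre-treatment lists.

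**Conclusion.** The concern holds in a limited form. Section 10.2 intends the same quantities before and after but takes them from different sources, and section 7.2 names hospital admissions and work absence only in the repeated follow-up interviews. With no control group, differential capture of these items cannot be separated from a treatment effect.

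The size and direction of the bias cannot be computed from the documents. The 11% to 100% range in the working is an illustration that assumes c between 0.9 and 0.5, a constant true rate and monthly scaling; it applies to the affected item, not to total expenditure. Confidence is medium because the Annex 3 form was not seen. The plan should be amended, or a sentence should confirm that the form already matches the two periods.

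**What to change.** Amend sections 7.2 and 10.2 as follows:

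1. At day 0, collect the section 10.2 items for the preceding 6 months, at least admission days and days and hours of absence. Use the same questions as in follow-up, alongside the doctor's records, and include hours as well as days in the follow-up questions.
2. Date each complication in the one-year history, so that only those in the 6-month window enter the comparison.
3. Name admissions and absence among the items that the doctor records in follow-up. Then add a sensitivity analysis restricted to the same source, the doctor's records, in both periods. Without the first part, that analysis could lose the two components in question.
4. If the Annex 3 form already does this, say so in both sections.

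The cost is one form page at a visit that already takes place, added items in the doctor's follow-up record, and a short amendment. Recall over 6 months at day 0 will leave some error relative to the shorter recall intervals of most follow-up contacts, and this should be acknowledged as a limitation. The change is best made early, since pre-treatment data become harder to recover with time.
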